8.1 Intent-to-Treat

The ITT population includes all randomized subjects. Subjects in the ITT population will be analyzed as randomized.

8.2 Per Protocol

The PP population includes subjects in the ITT population who do not have significant protocol deviations and who complete the study. Protocol deviations will be assessed prior to database lock and unmasking. Subjects in the PP population will be analyzed as treated.

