Clinical Trial Protocol

Protocol Title: Multicenter, Randomized, Controlled, Double-Masked Clinical Trial to Evaluate the Efficacy of OC-02 Nasal Spray on Signs and Symptoms of Dry Eye Disease

Protocol Number: OPP-001
Study Phase: 2
Product Name: OC-02 Nasal Spray
[REDACTED]
Indication: Dry Eye Disease
Investigators: Multi-Center

Sponsor: Oyster Point Pharma, Inc.
[name]
[name]

Contract Research Organization: [REDACTED]
[REDACTED] [REDACTED] [REDACTED]
[REDACTED]

Institutional Review Board: Alpha IRB
[name]
[name]
[name]

	Date
Original Protocol:	11 October 2017
Amendment 1:	N/A

Confidentiality Statement

This protocol contains confidential, proprietary information of [REDACTED] and/or Oyster Point Pharma, Inc. Further dissemination, distribution or copying of this protocol or its contents is strictly prohibited.

SPONSOR PERSONNEL

[REDACTED]	[REDACTED]
[REDACTED]	[REDACTED]
[REDACTED]	[REDACTED]
[REDACTED]	[REDACTED]

MEDICAL MONITOR

[REDACTED]	[REDACTED]
[REDACTED]	[REDACTED]
[REDACTED]	[REDACTED]
[REDACTED]	[REDACTED]
[REDACTED]	[REDACTED]
[REDACTED]	[REDACTED]

[REDACTED] PERSONNEL

[REDACTED]	[REDACTED]
[REDACTED]	[REDACTED]
[REDACTED]	[REDACTED]
[REDACTED]	[REDACTED]
[REDACTED]	[REDACTED]
[REDACTED]	[REDACTED]
[REDACTED]	[REDACTED]
[REDACTED]	[REDACTED]
[REDACTED]	[REDACTED]
[REDACTED]	[REDACTED]

SYNOPSIS

Protocol Title:	Multicenter, Randomized, Controlled, Double-Masked Clinical Trial to Evaluate the Efficacy of OC-02 Nasal Spray on Signs and Symptoms of Dry Eye Disease
Protocol Number:	OPP-001
Investigational Product:	OC-02 Nasal Spray
Study Objective:	The objective of this study is to evaluate the safety and effectiveness of OC-02 Nasal Spray as compared to placebo on signs and symptoms of dry eye disease (DED)
Overall Study Design	
Structure:	A Phase 2, multicenter, randomized, controlled, double-masked study
Duration:	Two study visits over approximately two weeks
Controls:	Placebo (OC-02 Vehicle Nasal Spray)
Dosing Regimen:	Treatment at Visit 1 and Visit 2
Summary of Visit Schedule:	
 • Visit 1 = Day 1, Screening and Treatment (Schirmer's Test Evaluation) • Visit 2 = Day 15 + 4, Treatment (Eye Dryness Score Evaluation)
Measures Taken to Reduce Bias:	This is a randomized, double-masked study
Study Population Characteristics	
Number of Subjects:	Approximately 160 (40 per arm)
Condition/Disease:	Dry Eye Disease

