8.3 Examination Procedures

8.3.1 Procedures to be Performed at Each Study Visit with Regard to Study Objectives(s)

The following procedures will be performed (see [Appendix 2](#) for description).

Visit 1 (Day 1): Screening and Schirmer's Test Evaluation

Screening

- Informed consent/Health Information Portability and Accountability Act (HIPAA) consent
- Demographic data, medical/medication, and ocular history
- Eligibility Criteria
- OSDI©
- EDS (visual analog scale)
- ██████████ Ocular Discomfort Scale
- BCVA
- Slit lamp biomicroscopy
- Corneal fluorescein staining
- Schirmer's Test³
- Schirmer's Test with nasal stimulation (cotton swab)⁴
- Intranasal examination
- Urine Pregnancy Test (if applicable)
- Concomitant Medications
- AE Query

Treatment (Schirmer's Test Evaluation)

Pre-Treatment Procedures:

- Randomization: Qualified participants will be assigned to one of the following treatment groups:
 - Placebo (vehicle) delivered as a 100 µL intranasal spray in each nostril
 - 0.11% OC-02 (0.2% hemigalactarate salt) delivered as a 100 µL intranasal spray in each nostril

³ Procedure will occur after corneal fluorescein staining

⁴ Schirmer's test with nasal stimulation will occur 10 minutes after the first Schirmer's test

- 0.55% OC-02 (1.0% hemigalactarate salt) delivered as a 100 µL intranasal spray in each nostril
- 1.1% OC-02 (2.0% hemigalactarate salt) delivered as a 100 µL intranasal spray in each nostril

Treatment Procedures:

- Instruct subjects on investigational drug / placebo administration
- Treatment with investigational drug/placebo

Post-Treatment Procedures:

- Post-treatment Schirmer's test (performed immediately after investigational drug administration)
- BCVA
- Slit lamp biomicroscopy
- Intranasal endoscopic examination
- Concomitant Medications
- AE Query
- Schedule participant for Visit 2

Visit 2 (Day 15+4): CAE

- Medical/medication and ocular history updates
- EDS
- Ora Calibra® Ocular Discomfort Scale
- Approximately 120 minutes of CAE® Exposure
- EDS collected upon entering the CAE® and every 5 minutes thereafter.
- ██████████ Ocular Discomfort Scale upon entering the CAE® and every 5 minutes thereafter.
- Instruct subjects on investigational drug/placebo administration
- Treatment with investigational drug/placebo

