8.6 Subject Disposition

8.6.1 Completed Subjects

A completed subject is one who has not be discontinued from the study.

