5.2 Unmasking

All subjects, Investigators, and study personnel involved with the conduct of the study will be masked with regard to treatment assignments. When medically necessary, the Investigator may need to determine what treatment arm has been assigned to a subject. When possible (i.e., in non-emergent situations), [REDACTED] and/or the Sponsor should be notified before unmasking study drug. Scratch off labels will be used to facilitate unmasking. The unmasked subject will be discontinued from the study.

6. Sample Size and Power Considerations

[REDACTED]

[figure not shown]
[REDACTED]

[REDACTED]

[REDACTED]

[REDACTED]

[REDACTED]

7. Data Preparation

All subject data will be captured in the subject source documents which will be transcribed in the eCRFs. The Investigator is responsible for ensuring that study data is completely and accurately recorded on each subject's eCRF, source documents, and all study-related materials. All study data should also be attributable, legible, contemporaneous, and original. Recorded datum should only be corrected in a manner that does not obliterate, destroy, or render illegible the previous entry (e.g., by drawing a single line through the incorrect entry and writing the revision next to the corrected data). An individual who has corrected a data entry should make clear who made the correction and when, by adding to the correction his/her initials as well as the date of the correction.

Data entry of all enrolled and randomized subjects will use software that conforms to 21 CFR Part 11 requirements, and will be performed only by staff who have been trained on the system and have access to the system. Data will not be entered for screen failure subjects. An audit trail will be maintained within the electronic system to capture all changes made within the eCRF database. After the end of the study and database lock, compact discs containing copies of all applicable subjects' eCRFs will be provided to each Investigator Site to be maintained on file by the Investigator.

8. Analysis Populations

[figure not shown]
Analysis populations include the intent-to-treat (ITT) population, the per-protocol (PP) population, and the Safety population. The statistical analysis of safety data will be performed for the safety population. The analysis of baseline and efficacy data will be performed for the ITT population. Efficacy analyses will also be performed for the PP population as sensitivity analyses.

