9.5 Adjustments for Multiplicity

Adjustments for multiple testing will not be implemented for this early phase study.

10. Disposition of Subjects

Subject disposition will be presented in terms of the numbers and percentages of subjects who were randomized, completed the study, and discontinued from the study. Subjects who are not discontinued from the study will be considered study completers. Disposition will be summarized by treatment group and for all subjects.

The number of randomized subjects in each of the analysis populations (ITT, PP and Safety) will be displayed by treatment. The ITT population uses treatment as randomized; PP and Safety populations use treatment as treated. Percentages are based on the total number of subjects randomized in each treatment group.

The number and percentage of subjects prematurely discontinued from the study and the reasons for study discontinuation will be summarized by treatment group for all randomized subjects. The reasons for study discontinuation that will be summarized include: AE, protocol violations, administrative reasons (e.g., inability to continue, lost to follow up), sponsor termination of study, subject choice, and other. In addition, any subject may be discontinued for any sound medical reason at the discretion of the Investigator (after consultation with the Sponsor) or Sponsor. A subject listing will be provided that includes the date of and reason for premature study discontinuation.

The number and percentage of subjects with any, major, and minor protocol deviations will be summarized by treatment group for all randomized subjects. The number and percentage of subjects with any protocol deviation will also be summarized for the following categories: Informed Consent, Inclusion / Exclusion and Randomization, Test Article / Study Drug Instillation and Assignment at Site, Improper Protocol Procedures at Site, Site's Failure to Report SAE / AE, Visit Out of Window, Subject's Non-compliance with Test Article, Subject's Use of Prohibited Concomitant Medication, Subject's Failure to Follow Instructions, and Other. A subject listing will be provided that includes the date and description of each deviation.

In addition, subject listings will be provided that include randomization and treatment; whether inclusion and exclusion criteria were met; and inclusion in the ITT, Safety, and PP populations.

11. Demographic and Pretreatment Variables

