14.1.1 SCHIRMER'S TEST

Schirmer's test with topical anesthesia will be performed pre- and post-treatment at Visit 1. Schirmer's test result will be summarized by time point (pre- and post-treatment at Visit 1), and treatment with quantitative descriptive statistics (n, mean, median, standard deviation, minimum and maximum).

 model will be used to compare the change in Schirmer's Test pre- to post-treatment in the study eye between each dose of OC-02 Nasal Spray and placebo treatment groups. The  model will include baseline Schirmer's Test (captured at Screening) and study

site as covariates. Least Squares Means (LS Means) for each treatment, the corresponding 95% confidence intervals (CI), and the estimated treatment differences between each dose of OC-02 Nasal Spray and placebo will be calculated from this [REDACTED] model. In addition, the study site by treatment interaction will be explored in a separate model to evaluate how the treatment effect may differ across study sites. In the case of a significant interaction at the 0.05 level, analyses will be performed by site to understand how the treatment effect differs across sites. The differences in means, two-sided 95% CIs for the difference in means and p-values will be reported. Pairwise t-tests from the ANCOVA model will be used to compare treatment and placebo groups.

The primary analyses will be performed on the ITT population on observed data only. The SAS code for the analysis is:

[REDACTED]

[REDACTED] analysis estimates of pre- to post-treatment changes will be displayed in a bar chart with standard error bars by treatment group. Two sample t-tests and non-parametric Wilcoxon rank sum tests will be used to compare treatments as unadjusted sensitivity analyses. The number and percentage of subjects with a greater than 10 mm and greater than 20 mm increases relative to baseline will also be reported by treatment group. The percentage of subjects in each treatment group will be compared using Fisher's Exact Test. Sensitivity analyses will also be performed on the ITT population with multiple imputation (MI) to impute missing data, as well as the PP population with observed data only.

[figure not shown]

The multiple imputation sensitivity analysis will use MCMC imputation to have a full accounting of the ITT population at Visit 1. The MCMC method will be performed using the SAS procedure PROC MI. The SAS code for obtaining multiple imputation data is:

```
[REDACTED SAS CODE]
```

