After obtaining twenty complete data sets and calculating changes from baseline, the following SAS code will be used to run the [REDACTED] model on each data set and combine the results from the twenty analyses:

```
[REDACTED SAS CODE]
```

[REDACTED]

Schirmer's test will also be analyzed in the fellow eye using the ITT and PP populations with observed data only.

Stratified analyses of Schirmer's test will include [REDACTED] analysis, t-tests and Wilcoxon rank sum tests using the ITT population with observed data only, in the study eye and fellow eye, separately. The following strata will be used:

[figure not shown]
- Inferior corneal staining < 1.5
- Inferior corneal staining ≥ 1.5
- Baseline EDS < 60
- Baseline EDS ≥ 60

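### The per-protocol Schirmer analysis requires completion through Visit 2, although the Schirmer endpoint is final on Day 1, so valid Visit 1 values can be dropped because of later events

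*SAP*

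**What the plan says.** SAP 8.2 limits the PP population to ITT subjects "who do not have significant protocol deviations and who complete the study". Protocol 10.1 gives the same rule. No readable section of either document gives a separate PP rule for each endpoint.

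The two documents define completion in the same way. Protocol 8.6.1: "A completed subject is one who has not be discontinued from the study". SAP Section 10 (Disposition of Subjects): "Subjects who are not discontinued from the study will be considered study completers". The protocol synopsis gives the duration as "Two study visits over approximately two weeks", and Protocol 8.3.1 and Appendix 1 place study exit at the end of Visit 2, Day 15 + 4.

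The Schirmer endpoint belongs to Visit 1. Protocol 8.3.1 has the post-treatment test "performed immediately after investigational drug administration".

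The PP set is then applied to that endpoint. SAP Section 8: "Efficacy analyses will also be performed for the PP population as sensitivity analyses". For the study eye, SAP 14.1.1 lists among the sensitivity analyses MI on the ITT population "as well as the PP population with observed data only" (Table 14.2.1.3). For the fellow eye, SAP 14.1.1 adds an analysis "using the ITT and PP populations with observed data only" (Table 14.2.1.12).

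**The concern.** A PP sensitivity analysis should show whether the result holds among subjects whose data for that endpoint were obtained as planned. For Schirmer, everything that matters has happened by the end of Visit 1: the basal test, randomization, the dose and the post-treatment test. Whether the subject is still in the study two weeks later says nothing about adherence at Visit 1. The completion rule nevertheless removes that subject, so the analysis is conditioned on an event after the outcome.

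The later event need not be unrelated to treatment. Protocol 8.6.2 lists adverse events and subject choice among the reasons for discontinuation. Protocol 9.4 and SAP 5.2 require discontinuation after unmasking. A reaction to the first dose could therefore lead to exclusion from the PP analysis of the response to that same dose. If PP and ITT then disagreed on Schirmer, the difference could not be attributed to adherence at Visit 1.

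**Working it through.** **Inputs.** Protocol 10.3: about 40 randomized per arm, four arms, 160 in total, 5% dropout, about 38 completers per arm. The readable text gives no Schirmer SD or effect size, so everything on bias below is in SD units and rests on assumed values.

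**Step 1: the plan's own figure.** Completers per arm = 40 × (1 − 0.05) = 38. This reproduces the stated 38. Total = 4 × 40 = 160.

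**Step 2: loss of subjects.** Non-completers per arm = 40 × 0.05 = 2; in total, 160 × 0.05 = 8. If every dropout comes after the post-treatment Schirmer, all of these have a valid value that the PP rule discards. This is an upper bound: a subject who leaves before that test has no value to lose, and a subject with a significant Visit 1 deviation would be excluded anyway.

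**Step 3: loss of precision.** Ratio of standard errors = sqrt(40/38) = 1.026, an increase of at most about 2.6% at the planned dropout.

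**Step 4: bias, if exclusion is related to outcome in one arm only.** Let f be the fraction excluded and D the completer-minus-excluded difference in mean, in SD units. The full-arm mean is the completer mean minus f × D, so restricting to completers shifts that arm by f × D. With the same f in both arms, the SE of the treatment difference is sqrt(2/(40 × (1 − f))).

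| f | SE (SD units) | D | Shift f × D | Shift / SE |
|---|---|---|---|---|
| 5% | 0.229 | 0.5 | 0.025 | 0.11 |
| 5% | 0.229 | 1 | 0.05 | 0.22 |
| 5% | 0.229 | 2 | 0.10 | 0.44 |
| 10% | 0.236 | 0.5 | 0.05 | 0.21 |
| 10% | 0.236 | 1 | 0.10 | 0.42 |
| 10% | 0.236 | 2 | 0.20 | 0.85 |

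**Step 5: extreme case.** Normal data, no true effect, two-sided t-test at 0.05, 50,000 simulated trials. One arm loses its lowest values and the other loses the same number at random.

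| Lowest values removed, of 40 | Rejection rate |
|---|---|
| 0 | 4.9% |
| 2 | 8.3% |
| 4 | 14.7% |

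This marks the edge of what is possible and is not a forecast.

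**Step 6: no relation to outcome, or the same pattern in every arm.** The treatment difference is not biased. The only cost is the 5% of subjects in Step 2.

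**The case against.** The strongest reply is that little depends on this analysis. The primary Schirmer analysis is ITT on observed data, so it keeps every subject with the required Visit 1 data, whatever happens later. PP is one sensitivity analysis beside MI, t-tests and Wilcoxon tests, and the SAP also lists tipping-point and pattern-mixture tables for this endpoint. SAP 3.4 calls the hypotheses exploratory, and no decision rule uses PP. Discontinuations, deviations and population counts are tabulated by arm, so a discrepancy caused by dropout could be traced. All of this stands, and it keeps the point small.

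A second reply is that one whole-study PP set is coherent, because success requires rejecting both null hypotheses and a common set shows both endpoints in the same subjects. This does not stand. Nothing in the documents requires a common PP set for the two endpoints, and completing Visit 2 is no evidence of adherence at Visit 1.

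A reader might also infer more than the documents support:

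- **That dropout will differ by arm because of the drug.** The protocol gives one flat 5% rate, expects little missing data (10.4.3) and states in the synopsis that instillation has no known risks. Unequal, treatment-related dropout is possible but hypothetical.
- **That 2 per arm is the expected loss.** It is the most that 5% dropout can produce, for the reasons in Step 2.
- **That Visit 2 deviations will remove Visit 1 data.** SAP 8.2 excludes only significant deviations, which the readable text does not define. This is possible, for example for a visit out of window, but not established.
- **That subjects who never qualify for the Visit 2 dose are lost as well.** Failing to qualify is not in itself discontinuation, so such a subject still counts as a completer.
- **That the fellow-eye PP table is a sensitivity analysis of the primary endpoint.** The efficacy unit is the study eye (SAP 9.1); the fellow-eye analysis is additional.

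**Conclusion.** The point holds as a minor flaw in the definition of a sensitivity population. Followed as written, SAP 8.2 drops valid, compliant Day 1 Schirmer values because of a later discontinuation, and no readable section prevents this. The masked review covers deviations, but the completion criterion applies whatever that review decides.

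At the planned dropout the direct cost is at most about 2 subjects per arm and 2.6% in standard error. Bias is conditional: it needs discontinuation that is related to the Schirmer result, with a pattern that differs between arms. Under the assumed differences of 0.5 to 2 SD it stays below half a standard error at 5% exclusion and below one at 10%. The primary result is not in question. What suffers is the meaning of the PP Schirmer tables.

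**What to change.** In SAP 8.2, define PP by endpoint:

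- **Schirmer:** ITT subjects who have the basal screening Schirmer test and the post-treatment Visit 1 Schirmer test, and no significant deviation affecting the Visit 1 assessment. No completion requirement. The two tests should be named, because Visit 1 also includes a third, with cotton-swab stimulation.
- **EDS:** keep the current rule (no significant deviations and study completion).

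Set both flags at the masked review before database lock, so that the choice cannot look data-driven. The SAP states that its methods supersede the protocol's, so the change can be made there and recorded in SAP Section 18.

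The cost is one extra population flag, and PP counts that differ between the two endpoints and need a footnote. No new data or procedures are needed.

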8.3 Safety

The Safety population includes all randomized subjects who have received at least one dose of the investigational product. Subjects in the Safety population will be analyzed as treated.

9. General Statistical Considerations

9.1 Unit of Analysis

Safety endpoints will be analyzed for both eyes. For efficacy endpoints, the unit of analysis will be the study eye as defined by the following:

The study eye is defined as the eye that meets all inclusion/exclusion criteria; if both eyes qualify then the eye with the greatest increase in tear production with stimulation by a cotton swab at the Screening Visit or, if there is no difference in stimulated tear production, the eye with the lower basal Schirmer's score at screening. If there is no difference for either measure, the right eye will be used as the study eye.

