 - Treatment with Investigational drug/placebo will be administered upon participant reporting an Ocular Discomfort score ≥ 3 at two or more consecutive time points in at least one eye during CAE® exposure (if a participant has an Ocular Discomfort rating of 3 at time = 0 for an eye, s/he must report an Ocular Discomfort rating of 4 for two consecutive measurements for that eye) using the ██████████ Scale. Participant will resume symptom assessments 1 minute after the application ends every 5 minutes.
- BCVA
- Slit lamp biomicroscopy

- Intranasal Examination
- Urine Pregnancy Test (if applicable)
- Concomitant Medications
- AE Query
- Study exit

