Please turn over the questionnaire to calculate the patient's final OSDI[®] score.

Evaluating the OSDI® Score¹

The OSDI® is assessed on a scale of 0 to 100, with higher scores representing greater disability. The index demonstrates sensitivity and specificity in distinguishing between normal subjects and patients with dry eye disease. The OSDI® is a valid and reliable instrument for measuring dry eye disease (normal, mild to moderate, and severe) and effect on vision-related function.

Assessing Your Patient's Dry Eye Disease^{1,2}

Use your answers D and E from side 1 to compare the sum of scores for all questions answered (D) and the number of questions answered (E) with the chart below.* Find where your patient's score would fall. Match the corresponding shade of red to the key below to determine whether your patient's score indicates normal, mild, moderate, or severe dry eye disease.

Eye Dryness Score (EDS) Using a Visual Analog Scale (VAS)

Participants will be asked the following question regarding eye dryness every 5 minutes during CAE[®] exposure.

The participant will be asked to rate their ocular symptoms (both eyes simultaneously) due to eye dryness by placing a vertical mark on the horizontal line to indicate the level of discomfort; 0 corresponds to “no discomfort” and 100 corresponds to “maximal discomfort.” The assessment line length of the scale will be 100 mm.

Please rate your current eye dryness by drawing a vertical line on the line below:

No Discomfort Maximal Discomfort

██████████ ■ Ocular Discomfort Scale

Ocular discomfort scores will be subjectively graded by the participants according to the following scale, rating each eye separately.

- 0 = No discomfort**
- 1 = Intermittent awareness**
- 2 = Constant awareness**
- 3 = Intermittent discomfort**
- 4 = Constant discomfort**

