14.1.2 EYE DRYNESS SCORE AS THE PRIMARY ANALYSIS

Eye dryness will be assessed pre-treatment at Visit 1, pre-CAE at Visit 2, and every 5 minutes during CAE® exposure at Visit 2. For each assessment, the participant will be asked to rate their ocular symptoms (both eyes simultaneously) due to eye dryness by placing a vertical mark on a 100 mm horizontal line to indicate the level of discomfort; 0 corresponds to "no discomfort" and 100 corresponds to "maximal discomfort".

Treatment with study drug will be administered upon the participant reporting an Ocular Discomfort ([REDACTED] Scale) score ≥ 3 at two or more consecutive timepoints in at least one eye during CAE® exposure. If a participant has an Ocular Discomfort rating of 3 at time = 0 for an eye, s/he must report an Ocular Discomfort rating of 4 for two consecutive measurements for that eye. Participant will resume symptom assessments 1 minute after the application ends every five minutes.

The primary analysis will be a one-timepoint analysis in which the pre-treatment EDS will be the EDS at the timepoint that the subject first qualifies for study drug administration during the CAE® and post-treatment EDS will be the EDS at the first timepoint following qualification. If a participant fails to qualify

for study drug administration, the timepoint of qualification and the pre-treatment and post-treatment EDS will be missing.

Eye dryness score will be summarized by visit, timepoint, and treatment with quantitative descriptive statistics (n, mean, median, standard deviation, minimum and maximum).

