[REDACTED] Ocular Discomfort Scale results will be summarized by timepoint at Visit 2 and treatment with quantitative descriptive statistics. Change from pre- to post-treatment in [REDACTED] Ocular Discomfort Scale results will also be summarized by timepoint (based on the timepoint from the pre-treatment assessment to the respective post-treatment assessment) at Visit 2 and treatment group with quantitative descriptive statistics in a manner similar to EDS. [REDACTED] models will be used that include pre-treatment ocular discomfort, timepoint of qualification, treatment and study site as covariates. [REDACTED] analysis estimates of pre- to post-treatment changes will be displayed graphically by timepoint

in a line plot by treatment group. Two sample t-tests and non-parametric Wilcoxon rank sum tests will be used to compare treatments as unadjusted sensitivity analyses.

15. Safety Analyses

All safety analyses will be conducted using the Safety population.

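### Either eye can trigger the Visit 2 dose, but ocular discomfort is by default analysed in the study eye, so some analysed eyes may not have reached the trigger (secondary endpoint only)

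*SAP*

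**What the plan says.** - **Trigger.** Protocol 8.3.1 gives the Visit 2 dose after an Ocular Discomfort "score ≥ 3 at two or more consecutive time points in at least one eye during CAE® exposure", and SAP 14.1.2 repeats the rule. The time-zero exception also works eye by eye (SAP 14.1.2: "rating of 3 at time = 0 for an eye, s/he must report an Ocular Discomfort rating of 4").
- **Scale.** Protocol Appendix 2: "Ocular discomfort scores will be subjectively graded by the participants according to the following scale, rating each eye separately". Grades run from 0 to 4.
- **Unit of analysis.** SAP 9.1: "For efficacy endpoints, the unit of analysis will be the study eye as defined by the following". The study eye must first meet the entry criteria. The rule continues: "if both eyes qualify then the eye with the greatest increase in tear production with stimulation by a cotton swab at the Screening Visit". Further ties go to the lower basal Schirmer's score and then to the right eye.
- **Endpoint.** SAP 3.1 lists ocular discomfort at Visit 2 as an additional efficacy measure, and SAP 14.2 lists it as secondary. In SAP 14.2.2, "models will be used that include pre-treatment ocular discomfort, timepoint of qualification, treatment and study site as covariates". That section and Tables 14.2.3.7 and 14.2.3.8 name no eye, so SAP 9.1 applies by default. By contrast, SAP 14.1.1 and the Schirmer's table titles do name the eye.
- **Not readable.** Eleven of the twelve inclusion criteria and protocol 10.4.2 (Unit of Analysis) are redacted.

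**The concern.** The analysis of change is anchored on the moment a subject becomes uncomfortable enough to be dosed, but that moment can be set by one eye and the change measured in the other. The readable tie-breaks for the study eye use tear measurements and eye side. None uses the Visit 2 discomfort scores.

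If the fellow eye alone meets the trigger, the analysed eye may start at 0, 1 or 2, while the eye rated 3 or 4 is left out. The possible improvement on this scale equals the starting grade, so a lower start limits what treatment can show. Adjusting for pre-treatment discomfort removes some variance but cannot create room to improve. At stake is sensitivity on the one symptom endpoint scored per eye, in a trial with about 38 completers per arm.

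**Working it through.** **1. The plan's own figure.** 40 per arm × 4 arms = 160, and 40 × (1 − 0.05) = 38 completers per arm. Both match protocol 10.3. The readable text gives no power, effect size or SD for discomfort, so there is no power figure to reproduce.

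**2. What follows from the rules.**

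| Eye(s) meeting the trigger | Study-eye score at qualification |
|---|---|
| Both, at the same time | 3 or 4 |
| Study eye only | 3 or 4 |
| Fellow eye only | Any grade |

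In the last row the study eye need not be comfortable. It may have a single rating of 3, or have started at 3 and not yet been rated 4 twice. The share of study eyes below 3 is therefore no larger than the share that had not met the trigger.

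**3. Simple share.** Let *d* be the share of dosed subjects in whom only one eye had met the trigger. If that eye is equally likely to be either one, the study eye is the wrong one in *d*/2. The documents do not give *d*. Assuming *d* = 10%, 20%, 30% or 40%, *d*/2 = 5%, 10%, 15% or 20%. Multiplied by 38, that is 1.9, 3.8, 5.7 or 7.6 subjects per arm if every completer is dosed.

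**4. Simulated share.** Taken from the documents: scores every 5 minutes over 120 minutes (120/5 + 1 = 25 scores) and the stated trigger with its time-zero exception. Assumed: discomfort rises during exposure, the study eye is unrelated to symptoms, and between-eye correlation is 0.5 to 0.95.
- With error SD of 0.3 or 0.6 grade and between-eye error correlation of 0 to 0.9, the study eye was below 3 at qualification in 17% to 41% of dosed subjects.
- In a similar model at correlation 0.95 with mostly shared noise, the share was 13% to 17%.

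The overall range is 13% to 41%, or 0.13 × 38 = 4.9 to 0.41 × 38 = 15.6 subjects per arm if all are dosed. As a plausibility check, when the study eye is unrelated to symptoms the share of subjects with exactly one eye at 3 or above is twice this: 26% to 82%. The upper end needs marked disagreement between two eyes in the same chamber.

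**5. Effect on the treatment difference.**
- Relief proportional to underlying severity: the study-eye difference was smaller by about 2–3% at correlation 0.95, 6–7% at 0.8 and 12–13% at 0.5.
- Constant relief: it hardly changed.

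The range is therefore about 0% to 13%.

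**6. Effect on sensitivity.** The ANCOVA test statistic was about 3% to 22% larger in the qualifying eye than in the study eye, in every setting tried (correlation 0.5 to 0.95, independent or mostly shared noise). For illustration, suppose the qualifying-eye analysis had 80% power at two-sided 0.05, so the expected z is 1.960 + 0.842 = 2.802. Then 2.802/1.03 = 2.72 and 2.802/1.22 = 2.30, giving study-eye power of Φ(2.72 − 1.96) = 78% and Φ(2.30 − 1.96) = 63%. The plan makes no power claim, so this only puts the ratios on a familiar scale.

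**The case against.** The strongest case against acting has four parts.

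- **Redaction.** A hidden inclusion criterion might tie the study eye to symptoms. That stands as a caution: a reader might infer that the study eye is never chosen on symptoms, and the documents cannot show it. But an entry criterion applied at screening would not make the study eye the first to cross the threshold at Visit 2. SAP 9.1 is readable, and the SAP says its methods supersede the protocol's.
- **Size.** A reader might infer that at least a quarter of study eyes fall below 3, or that the effect shrinks by 9% to 16%. The second figure comes from simulated ratios of mean pre-treatment score, study eye to qualifying eye, of 0.91 and 0.84 (1 − 0.91 = 9%; 1 − 0.84 = 16%). Neither is supported. Shared noise brings the share down to 13%. The ratio also treats observed score as severity, although the qualifying eye is selected for a high observed score, part of which is noise.
- **Floor.** A reader might picture many eyes starting at 0. In the simulations 0% to 4% did, and most eyes below 3 were at 2, which leaves two grades of room.
- **Consequence and remedy.** The endpoint is secondary, and success rests on Schirmer's test and EDS, whose hypotheses SAP 3.4 itself calls exploratory. Replacing an eye fixed before randomisation with one picked after the Visit 1 dose is debatable. This stands, and it is why the qualifying-eye analysis should be added beside the study-eye analysis rather than replace it.

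**Conclusion.** The mismatch is in the text, and following the plan can put into the discomfort analysis eyes that had not met the dosing trigger. It is a cheap improvement to a secondary endpoint.

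Three stronger conclusions are not supported:
- **That this does happen at a known rate.** No document reports between-eye agreement. The problem vanishes if both eyes always qualify together or the triggering eye is always the study eye.
- **That it biases the arms.** The study eye is fixed before randomisation and the model adjusts for pre-treatment discomfort. The harm is lost sensitivity.
- **That it touches the primary endpoints.** EDS is one rating covering both eyes, and Schirmer's test is measured at Visit 1.

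The 13% to 41% of study eyes below 3, and the 0% to 13% smaller difference, rest on the assumed correlation, noise and form of relief, and on a study eye unrelated to symptoms.

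**What to change.** In SAP 14.2.2:
1. State which eye the discomfort analysis uses, and keep the study-eye analysis.
2. Add a prespecified analysis of change in ocular discomfort in the qualifying eye, meaning the eye that met the Visit 2 trigger. If both met it at the same time, use the higher-scoring eye, and if still tied, the study eye. Use the same covariates, and report it beside the study-eye result.
3. Report, per arm, how many subjects had a study eye that had not met the trigger.

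The cost is one derivation from scores already rated in both eyes, and one table. The dosing rule and visit procedures are unchanged. There is one limitation to state: the qualifying eye is determined at Visit 2 (Day 15 + 4, so 14 to 18 days after Day 1), after the Visit 1 dose. Its between-arm comparison therefore assumes negligible carry-over.
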